3.3. Strata and Covariates

Subjects will be randomly assigned to treatment groups via the interactive web response system (IWRS) using a stratified randomization schedule into each individual study (Cohort A Induction Study, Cohort B Induction Study, and Maintenance Study). Details of the randomization ratio and stratification variables for each study are provided in Section 1.2.

If there are discrepancies in stratification factor values between the IWRS and the clinical database, the baseline values recorded in the clinical database will be used for analyses. For deriving concomitant medication use at Day 1, the start date of such medication should be before or on the same date of the first dose of study drug and with either the stop date of such medication being on or after the first dose of study drug or with ‘ongoing’ status.

Stratification factors will be used as covariates in evaluating efficacy endpoints, as specified in Section 6.

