3.5. Multiple Comparisons

The graphical approach {Bretz 2009} to sequentially rejective multiple test procedures will be used to control a family-wise type I error rate (FWER) at 5% (ie, $\alpha = 0.05$) for each individual study (Cohort A Induction Study, Cohort B Induction Study, and Maintenance Study). This procedure strongly protects the FWER on all the primary and key secondary endpoints.

Induction Studies (Cohort A Induction Study and Cohort B Induction Study)

For each individual study (Cohort A Induction Study, Cohort B Induction Study, and Maintenance Study), a Bonferroni approach with equal alpha allocation of 0.025 (2-sided) to each filgotinib dose group comparison with placebo will be used to control the overall study-wide type I error rate at 0.05 within each study. To protect the integrity of the study due to the unblinded interim futility analysis planned for each induction study (Cohort A Induction Study and Cohort B Induction Study), an alpha of 0.00001 will be spent for each filgotinib dose group comparison to placebo within each induction study. As a result, a nominal p-value of less than 0.02499 (2-sided) will be needed to declare statistical significance for the final primary analysis of each filgotinib dose group when compared to placebo to control the study-wise type I error rate at 0.05. If one filgotinib dose group is discontinued for futility at the interim futility analysis, the overall alpha error rate stays unchanged at a 2-sided 0.02499 level for the continuing filgotinib dose group at the primary analysis.

The hypotheses to be tested for the induction studies are outlined below.

The primary null hypotheses to be tested:

- H1: The EBS remission rate in the filgotinib 200 mg group is equal to the EBS remission rate in the placebo group at Week 10
- H2: The EBS remission rate in the filgotinib 100 mg group is equal to the EBS remission rate in the placebo group at Week 10

[figure not shown]
The key secondary null hypotheses to be tested:

- H3: The MCS remission rate in the filgotinib 200 mg group is equal to the MCS remission rate in the placebo group at Week 10
- H4: The MCS remission rate in the filgotinib 100 mg group is equal to the MCS remission rate in the placebo group at Week 10
- H5: The endoscopic subscore of 0 rate in the filgotinib 200 mg group is equal to the endoscopic subscore of 0 rate in the placebo group at Week 10

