6.2.3. Analysis of the Primary Efficacy Endpoint

For the individual Induction Studies (Cohort A Induction Study and Cohort B Induction Study), a stratified Cochran-Mantel-Haenszel (CMH) test will be used to compare the treatment effect between the filgotinib 200 mg group and placebo and between the filgotinib 100 mg group and placebo separately. The CMH tests will be stratified by the following factors:

- Concomitant use of oral, systemically absorbed corticosteroids at Day 1
- Concomitant use of immunomodulators at Day 1
- Exposure to biologic agent as listed in [Appendix 2](#) (≤ 1 , > 1 ; for Cohort B Induction Study only)

For the Maintenance Study, a CMH test will be used to compare the treatment effect between filgotinib 200 mg and placebo among the subjects from the Cohort A and B Induction Studies combined being treated with filgotinib 200 mg. The CMH test will be stratified by the following factors:

- Participation in Cohort A or Cohort B
- Concomitant use of oral, systemically absorbed corticosteroids at re-baseline
- Concomitant use of immunomodulators at re-baseline

Similarly, a CMH test with the same stratification factors will be used to compare the treatment effect between filgotinib 100 mg and placebo among the subjects from the Cohort A and B Induction Studies combined being treated with filgotinib 100 mg.

The stratified CMH chi-square p-value will be provided for each of the above comparison. Strata with low numbers of subjects might be aggregated for the CMH test. The 2-sided 95% confidence interval (CI) of EBS remission rate based on normal approximation method with a continuity correction will be provided for each treatment group. In addition, non-stratified risk difference estimated along with its 2-sided 95% CI using the normal approximation (ie, the Wald method) with a continuity correction for the difference in proportions will be provided. Reference Section 3.5 for the significance level that will be used to declare a statistically significant treatment effect for each filgotinib group. Stratification variables based on the eCRF data will be used for the analysis.

Bar-charts of proportions of subjects achieving EBS remission at Week 10 and Week 58 will be provided by treatment group with corresponding p-values. In addition to the primary analysis method described above, the proportion of subjects in EBS remission who had a stool frequency subscore of 0 versus 1 will be calculated and summarized.

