6.2.4. Sensitivity Analysis of the Primary Efficacy Endpoints

Sensitivity analyses of the primary efficacy endpoint will be performed for each individual study (Cohort A Induction Study, Cohort B Induction Study, and Maintenance Study). For all of the sensitivity analyses, the same statistical method that was used for the primary analysis, will be used for the treatment comparison.

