6.2.4.4. Analysis Excluding US/Korea Non-Dual Refractory Males

Given the restriction in the US/Korea of only allowing dual refractory males to receive filgotinib 200 mg, there exists an inherent imbalance in the Cohort B Induction Study between subjects randomized to filgotinib 200 mg and the placebo group with respect to US/Korea non-dual refractory males who will be present in the placebo group, but not in the filgotinib 200 mg group. Recognizing this imbalance and the theoretical potential for non-dual refractory subjects to have better disease prognosis and a higher chance of response, a sensitivity analysis excluding US/Korea non-dual refractory males from the placebo group in the FAS for Cohort B Induction Study will be conducted using the stratified CMH test for the treatment comparison between the filgotinib 200 mg and the placebo group on EBS remission at Week 10. This analysis will be the primary analysis for evaluating the efficacy of the filgotinib 200 mg dose group in the Cohort B Induction Study in support of a Japanese marketing application.

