For a subject, if the value of the grouping variable cannot be determined, this subject will be excluded from the corresponding subgroup analysis. Non-stratified risk difference between treatment groups will be evaluated for each of the subgroups using Fisher's exact test. A forest plot will graphically present the non-stratified risk difference and 95% CI using normal approximation with a continuity correction on the treatment differences (filgotinib placebo) in EBS remission rates for each of the subgroups.

Additional subgroup analyses for geographic region may be added based on the distribution of study enrollment prior to study unblinding.

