6.3.2. Analysis Methods for Secondary Efficacy Endpoints

The same statistical method that was described under Section 6.2.3 for testing the primary efficacy endpoint will be utilized for testing the key secondary efficacy endpoints. The key secondary efficacy endpoints will be tested in the order listed in Section 3.5. The key secondary efficacy endpoints will be tested only after the primary efficacy endpoint is shown to be statistically significant at the significance level specified in Section 3.5. Each key secondary efficacy endpoint will be tested at the same significance level that is used for the primary efficacy endpoint; testing will be stopped after the first failure to reject the null hypothesis of no difference for statistical inference. If the null hypothesis testing for the primary efficacy endpoint is not rejected, the key secondary efficacy endpoint comparisons will be considered exploratory.

Bar-charts of proportions of subjects achieving each of the key secondary efficacy endpoints by treatment group with corresponding p-values will be provided.

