6.4.2. Analysis of Exploratory Efficacy Endpoints

6.4.2.1. Analysis of dichotomous efficacy endpoints

A stratified CMH test will be used to compare the percentage difference of subjects between each filgotinib group and placebo group. The CMH chi-square nominal p-value will be provided. The 2-sided 95% CI based on normal approximation method will be provided for each treatment group. In addition, non-stratified risk difference estimated along with its 95% 2-sided CI with a continuity correction will be provided.

Bar-charts of proportions of subjects achieving the exploratory event type efficacy endpoints will be provided by treatment group with corresponding nominal p-values.

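### SAP 6.2.3 pairs a stratified CMH test with an unstratified, continuity-corrected Wald interval that is valid but mildly conservative; a stratified Newcombe interval would be a free improvement

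*SAP*

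**What the plan says.** For the primary endpoint, SAP 6.2.3 compares each dose with placebo by a stratified CMH test and reports the CMH p-value. It allows sparse strata to be aggregated. For the size of the effect it adds a "non-stratified risk difference estimated along with its 2-sided 95% CI using the normal approximation (ie, the Wald method) with a continuity correction". No Mantel-Haenszel difference, common odds ratio or other stratified estimate is planned.

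Elsewhere in the SAP:

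- Section 6.4.2.1 (exploratory dichotomous endpoints) repeats the estimate: "non-stratified risk difference estimated along with its 95% 2-sided CI with a continuity correction will be provided".
- Section 6.2.5 (subgroup forest plot) uses a non-stratified difference with a "95% CI using normal approximation with a continuity correction on the treatment differences".
- Section 6.2.4 (sensitivity analyses) says that "the same statistical method that was used for the primary analysis, will be used for the treatment comparison", and Section 6.3.2 (key secondary endpoints) says "The same statistical method that was described under Section 6.2.3 for testing the primary efficacy endpoint will be utilized". Both carry over the test. Neither expressly states which estimate and interval go with it.
- Section 3.5 sets the decision rule for induction: "a nominal p-value of less than 0.02499 (2-sided) will be needed to declare statistical significance for the final primary analysis". In Maintenance the level is 0.025 for each dose.

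**The concern.** Readers will quote the risk difference and its interval beside the CMH p-value. As planned, the two come from different analyses: the test conditions on the strata and the estimate ignores them. The continuity correction also adds a fixed amount to each side of the interval, so coverage exceeds 95% and the result looks less precise than the data allow. The added amount depends on the reciprocals of the arm sizes, so it matters most on the forest plot, where some subgroups may be small. What is at stake is the quality of the reported effect size, not the conclusion of any test.

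**Working it through.** **Inputs.** From SAP 1.3: induction 260 vs 130 at 25% vs 10%; Maintenance 190 vs 95 at 40% vs 20%; two-sided 0.025 for each comparison. Subgroup sizes and stratum shares are not in the documents; where used, they are assumptions.

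**The plan's own figure.** Induction power is stated as 90%. The pooled rate is (260×0.25 + 130×0.10)/390 = 0.20. The null SE is √[0.2×0.8×(1/260 + 1/130)] = 0.04297 and the alternative SE is √(0.25×0.75/260 + 0.1×0.9/130) = 0.03760. The critical value is 2.2414 and the continuity term is ½(1/260 + 1/130) = 0.00577.

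- Without correction: (0.15 − 2.2414×0.04297)/0.03760 = 1.428, power 92.3%.
- With correction: (0.15 − 0.00577 − 2.2414×0.04297)/0.03760 = 1.275, power 89.9%, which reproduces the stated 90%.

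The same formulas give 89.2% and 86.3% for Maintenance, both consistent with the stated more than 85%.

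**The planned interval.** d ± {1.96√[p₁(1−p₁)/n₁ + p₂(1−p₂)/n₂] + ½(1/n₁ + 1/n₂)}. At the planning rates:

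- Induction: Wald half-width 1.96×0.03760 = 7.37 points, plus 0.58 points of correction per side.
- Maintenance: 1.96√(0.4×0.6/190 + 0.2×0.8/95) = 10.64 points, plus 0.79 points per side.

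**Exact coverage and mean width**, summed over all pairs of binomial outcomes:

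| Setting | Planned | Wald, no correction | Newcombe |
|---|---|---|---|
| Induction, 260 vs 130 | 96.3%, 15.8 | 94.8%, 14.7 | 95.1%, 14.9 |
| Maintenance, 190 vs 95 | 96.2%, 22.8 | 94.7%, 21.2 | 94.9%, 21.1 |
| Subgroup 80 vs 40 (assumed) | 97.2%, 29.9 | 94.0%, 26.2 | 95.5%, 27.3 |
| Subgroup 40 vs 20 (assumed) | 97.8%, 43.9 | 93.9%, 36.4 | 95.9%, 39.2 |
| Subgroup 20 vs 10 (assumed) | 98.1%, 64.8 | 94.0%, 49.8 | 95.7%, 56.0 |

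Subgroup rows use 25% vs 10%; widths are in percentage points. For induction sizes, over placebo rates of 2–20% and differences of 0–20 points, the planned interval covers 96.1–97.6% and never falls below 95%.

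**With strata** (simulation; assumed stratum shares and rates). The stratified Newcombe interval covers 95.5–95.7% with width 15.0–15.1 points in induction, and 95.2% with width 21.2 in Maintenance. The planned interval is therefore about 5% and 7% wider. The SD of the stratified and unstratified estimates is the same (3.73–3.75 points in induction, 5.42 in Maintenance), so the gain comes from the form of the interval and not from adjustment.

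**Agreement with the test.** The share of trials in which the 95% interval excludes zero while the test is not significant is 3.3% (planned) and 3.2% (unstratified Newcombe) in induction, and 3.7% and 4.4% in Maintenance. The disagreement comes mainly from setting a 95% interval beside a test at 0.02499 or 0.025.

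**The case against.** The other side has a good case. An unstratified risk difference is a legitimate marginal summary, it is fully pre-specified, and its interval errs on the safe side. The decision rests on the CMH p-value under SAP 3.5, so no inference changes. In induction the saving is under one point of total width. All of this stands, and it is why the point is optional.

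A reader might also infer several stronger things that the documents do not support:

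- *That SAP 3.3 is contradicted.* It says "Stratification factors will be used as covariates in evaluating efficacy endpoints", but the sentence goes on to defer to Section 6 for how. Section 6.2.3 then specifies a stratified test and, in addition, an unstratified difference.
- *That the estimate is expressly prescribed for the sensitivity and key secondary analyses.* Sections 6.2.4 and 6.3.2 speak of the treatment comparison and the testing method only.
- *That a stratified interval would bring interval and test into line.* The disagreement figures show that it barely changes matters.
- *That stratifying would repair the allocation imbalance.* SAP 6.2.4.4 says "there exists an inherent imbalance in the Cohort B Induction Study between subjects randomized to filgotinib 200 mg and the placebo group", because US/Korea males who are not dual refractory cannot receive 200 mg. Cohort A has the same restriction: protocol 4.3.2 excludes prior TNFα antagonist and vedolizumab use, so every US/Korea male there falls under the two-arm allocation in SAP 1.2.1. Neither region nor sex is a CMH stratum. Any figure for the resulting shift in Cohort B would need inputs that the documents do not give, so none is offered as evidence here.

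**Conclusion.** The point holds as a minor reporting improvement. At the planning values the interval covers 1.3 points more than nominal in induction (96.3% vs 95%) and 1.2 points more in Maintenance (96.2% vs 95%), and it is 0.9 points (15.8 − 14.9) and 1.7 points (22.8 − 21.1) wider than Newcombe. The excess is larger in small subgroups: 8.8 points of width (64.8 − 56.0) at 20 vs 10. The interval is not invalid, and type I error, power and the test decision are untouched. The induction and Maintenance figures are exact at the planning rates in SAP 1.3. The subgroup figures rest on assumed sizes, and the stratified figures on assumed stratum shares and rates. With balanced strata, the precision of the estimate itself hardly changes.

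**What to change.** - In SAP 6.2.3, report the Mantel-Haenszel stratified risk difference over the same strata as the CMH test, with any aggregation carried through, and a stratified Newcombe 95% interval without continuity correction. Keep the unstratified difference as a supplement if wanted.
- State the same estimate explicitly for the sensitivity analyses (6.2.4), key secondary endpoints (6.3.2) and exploratory dichotomous endpoints (6.4.2.1).
- In the 6.2.5 forest plot, use an unstratified Newcombe interval.
- Do not simply delete the correction from the Wald interval: coverage would fall to 94.7–94.8% at the planned sizes and about 94% in the assumed subgroups.
- Label the 95% intervals nominal, since significance is judged at the levels in SAP 3.5.
- Keep the 6.2.4.4 analysis; this change does not replace it.

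The cost is SAP wording and routine programming. No new data are needed, and the test, alpha and sample size stay as they are.

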6.2.4. Sensitivity Analysis of the Primary Efficacy Endpoints

Sensitivity analyses of the primary efficacy endpoint will be performed for each individual study (Cohort A Induction Study, Cohort B Induction Study, and Maintenance Study). For all of the sensitivity analyses, the same statistical method that was used for the primary analysis, will be used for the treatment comparison.

6.2.4.1. Per-Protocol Analyses

To evaluate the impact of study conduct on the primary analysis, the primary endpoint of EBS remission rates of each individual study will be analyzed based on the corresponding PP analysis sets as defined in Section 3.1.3.

6.2.4.2. Locally Read Endoscopic Subscore Analyses

To evaluate the potential disparity between centrally read endoscopy scores versus locally read scores, the EBS remission rates using locally (ie, investigator) read endoscopic subscore will be analyzed based on the FAS.

6.2.4.3. Missing Data Imputation Analyses

Subjects who do not meet EBS remission due to study treatment failure or due to meeting protocol-specified disease worsening criterion will not be considered as missing in this section, but will be considered as not achieving EBS remission for the sensitivity analysis listed here.

To explore the distribution of the missing data across cohorts and treatment groups, missing EBS, MCS, and pMCS at Week 10 for Induction Studies and at Week 58 for Maintenance Study by baseline/re-baseline characteristic and disease status (severity/duration) including variables listed from below, in each treatment group will be summarized.

Cohort A Induction Study at Baseline

- Duration of UC (years)
- MCS score
- Endoscopic subscore of 3 (yes, no)
- Concomitant use of oral, systemically absorbed corticosteroids (yes, no)
- Concomitant use of immunomodulators (yes, no)

Cohort B Induction Study at Baseline

- Duration of UC (years)
- MCS score
- Endoscopic subscore of 3 (yes, no)
- Concomitant use of oral, systemically absorbed corticosteroids (yes, no)
- Concomitant use of immunomodulators (yes, no)
- Exposure to biologic agent listed in [Appendix 2](#) (≤ 1 , > 1)

Maintenance Study

- Duration of UC at baseline (years)
- MCS score at re-baseline
- Endoscopic subscore of 3 (yes, no) at re-baseline
- Concomitant use of oral, systemically absorbed corticosteroids at re-baseline (yes, no)
- Concomitant use of immunomodulators at re-baseline (yes, no)
- Participation in Cohort A or Cohort B

To evaluate the impact from missing data on the EBS remission rates at Weeks 10 and 58, the following missing value imputations will be used:

- 1) Observed-cases only imputation: Observed cases will be used for analysis without any imputation. Only subjects in the FAS with both baseline and Week 10 (or Week 58) data will be included for analysis.
- 2) Missing Success: impute subjects in the FAS who did not have sufficient data to decide on EBS remission as achieving the event.

- 3) Missing Success for placebo group and Missing Failure for filgotinib groups: impute subjects in the FAS who did not have sufficient data to decide on EBS remission as achieving this event for placebo group and as not achieving this event for filgotinib groups.
- 4) Using multiple imputation method to impute subjects in the FAS who did not have sufficient data to decide on EBS remission status. The EBS remission status for subjects who have missing data at Week 10 for Induction Studies or Week 58 for the Maintenance Study will be imputed in the multiple imputation procedure. A logistic regression model will be utilized to perform the imputation. The baseline values of EBS subscores (endoscopic, rectal bleeding and stool frequency subscores), treatment and stratification factors will be used as the independent variables in the model.

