### 3.6. Disease Worsening Criteria

Subjects meeting the following disease worsening criteria evaluated starting at Week 11 must be discontinued from blinded treatment and will be offered the option to receive open-label filgotinib by entering into the separate LTE study (GS-US-418-3899).

- Disease worsening starting at 11 weeks of therapy is based on the following criteria: partial MCS score (all components of MCS except for endoscopic subscore) increase of  $\geq 3$  points to at least 5 points from the Week 10 value on two consecutive visits, or an increase to 9 points on two consecutive visits if the Week 10 value is  $> 6$ .
  - The disease worsening visits may include unscheduled visits (eg, a study visit followed by an unscheduled visit, or 2 sequential unscheduled visits anytime from Week 11 onward).
- Disease worsening to the extent that the subject clinically requires medications prohibited by the study (at investigator discretion, with discussion with medical monitor if feasible); these subjects do not qualify for the LTE study.

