#### **6.6. Early Termination Assessments**

The following will be performed and documented:

- Symptom directed PE
- Obtain body weight and vital signs (resting blood pressure, respiratory rate, pulse and temperature)
- Perform 12-Lead ECG (for subjects who terminate prior to Week 10)
- Review AEs and concomitant medications
- Collect e-Diary back from subject
- Collect the variables to calculate partial MCS (see [Appendix 4](#))
  - Site collects patient assessments at each visit
  - MCS calculated centrally after all components have been captured electronically
- Obtain fasting blood samples (reference Study Procedure Table in [Appendix 2](#))
- Obtain urine sample (reference Study Procedures Table [[Appendix 2](#)])
  - Pregnancy test (for females of child bearing potential only)

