6.4.2.2. Analysis of MCS and pMCS exploratory endpoints

For calculation of MCS and pMCS, please refer to rules described under [Section 6.1.1](#) for MCS and pMCS with subscores.

MCS at screening will serve as induction baseline MCS. Partial MCS at Day 1 will serve as induction baseline pMCS. If pMCS at Day 1 is missing, the screening partial MCS will be used as induction baseline.

MCS at Week 10 will serve as maintenance re-baseline MCS. Partial MCS at Maintenance Day 1 will serve as Maintenance re-baseline pMCS. Re-baseline values of MCS and partial MCS will serve as Maintenance Study baseline for change from baseline calculation.

As 2 of the 3 partial MCS components (stool frequency and rectal bleeding) will be collected through the subject daily diary, partial MCS will be calculated at all visits when PGA is scheduled to be assessed.

Descriptive statistics will be used to summarize the absolute values and change from baseline values in MCS, endoscopic subscore, stool frequency subscore, rectal bleeding subscore, PGA and partial MCS by analysis visit and treatment group for Cohort A Induction Study, Cohort B Induction Study, and Maintenance Study. Shift tables of MCS subscores from baseline to Week 10 for Induction Studies and from Week 10 to Week 58 for Maintenance Study will be provided.

Difference of mean change from baseline at Week 10 for Induction Studies and difference of mean change from re-baseline at Week 58 for Maintenance study between each filgotinib dose group and placebo for partial MCS will be tested in an exploratory fashion using an analysis of covariance (ANCOVA) model adjusting for stratification factors and baseline or rebaseline value, respectively. Last Observation Carried Forward (LOCF) approach will be used to impute the missing values. Estimated means of treatment effects and estimated differences in treatment effects between each filgotinib treatment group and the placebo group will be presented with 95% CIs and nominal p-values. Difference of mean change from baseline (or re-baseline) for partial MCS at Weeks 2, 4, and 6 for Induction Studies and at Weeks 14, 20, 26, 34, 42 and 50 for Maintenance Study will be analyzed in the same fashion. The model based estimated mean change from baseline (or re-baseline) with 95% CIs will be plotted over all analysis visits by treatment group.

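### The multiple-imputation sensitivity analysis leaves out on-treatment symptom scores, so dropouts not already classed as failures, mainly in Induction, are imputed too favourably in both arms

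*SAP*

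**What the plan says.** SAP 6.2.4.3 gives four ways of handling missing EBS remission at Week 10 or Week 58: observed cases, all missing as success, success for placebo with failure for filgotinib, and multiple imputation. Item 4 is described as "Using multiple imputation method to impute subjects in the FAS who did not have sufficient data to decide on EBS remission status", and its model is specified in full: the three EBS subscores at baseline, "treatment and stratification factors will be used as the independent variables in the model".

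The section opens with an exclusion. Subjects who miss remission "due to study treatment failure or due to meeting protocol-specified disease worsening criterion will not be considered as missing in this section"; they count as not achieving remission in every analysis listed there.

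On-treatment scores exist. SAP 6.4.2.2 says that "partial MCS will be calculated at all visits when PGA is scheduled to be assessed", and it analyses "partial MCS at Weeks 2, 4, and 6 for Induction Studies and at Weeks 14, 20, 26, 34, 42 and 50 for Maintenance Study". Protocol 6.6 adds an early-termination assessment ("Collect the variables to calculate partial MCS") and lists no endoscopy there. Two of the three EBS components, stool frequency and rectal bleeding, are therefore usually on record for someone whose Week 10 or Week 58 EBS status is missing.

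The worsening rule is limited in time. Protocol 3.6 states: "Subjects meeting the following disease worsening criteria evaluated starting at Week 11 must be discontinued from blinded treatment".

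**The concern.** Item 4 is the only model-based missing-at-random analysis of the primary endpoint. With arm, strata and baseline subscores as its only predictors, it assumes that among subjects alike on those, leaving is unrelated to how treatment was going. That is hard to defend when symptoms during treatment plausibly drive both dropout and remission. A subject who leaves at Week 6 still bleeding, without having started or escalated a drug that triggers SAP Appendix 5, is imputed at roughly the observed rate for the arm and baseline profile. In that form item 4 adds little to item 1, the observed-case analysis.

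In Maintenance it is also unclear what the baseline EBS subscores in the model are. SAP 3.8.1.2 makes re-baseline the default. SAP 6.2.1 uses screening subscores to evaluate EBS remission. Item 4 does not say which applies.

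**Working it through.** **1. Planning figures (SAP 1.3).** Induction: 130 placebo v 260 filgotinib, 10% v 25%, two-sided 0.025, stated power 90%. With a continuity correction:
- corrected difference = 0.15 − 0.5 × (1/130 + 1/260) = 0.1442
- null SE = √[0.20 × 0.80 × (1/130 + 1/260)] = 0.0430
- alternative SE = √[0.10 × 0.90/130 + 0.25 × 0.75/260] = 0.0376
- power = Φ[(0.1442 − 2.241 × 0.0430)/0.0376] = 89.9%

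The stated 90% reproduces (92.3% without the correction). Maintenance (95 v 190, 20% v 40%) gives 86.3% with the correction, consistent with the stated figure of more than 85%. The SAP gives no figure for item 4.

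**2. Induction simulation.** Arm sizes and rates are as above. The documents give no dropout rate, so 5%, 10% and 20% overall are assumed. Also assumed: a Week 6 score correlated 0.7 with the latent Week 10 outcome, and logistic dropout driven by a poor Week 6 score. There were 300 replicates with 10 imputations each. Strata were not modelled, and no dropout was pre-classified as a treatment failure. Figures are percentages, filgotinib/placebo.

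| Dropout | Missing | True | Baseline-only MI | MI with Week 6 | NRI |
|---|---|---|---|---|---|
| 5% | 4.1/6.7 | 24.9/9.8 | 25.7/10.3 | 24.9/9.8 | 24.6/9.7 |
| 10% | 8.3/13.4 | 24.9/9.9 | 26.4/11.1 | 24.9/10.0 | 24.2/9.6 |
| 20% | 17.3/25.8 | 25.0/10.0 | 28.1/12.4 | 25.0/10.2 | 23.3/9.2 |

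Remission rate among filgotinib dropouts (%):

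| Dropout | True | Baseline-only MI | MI with Week 6 |
|---|---|---|---|
| 5% | 7.0 | 24.7 | 7.2 |
| 10% | 8.4 | 25.7 | 8.2 |
| 20% | 9.6 | 27.6 | 9.6 |

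At 10% dropout the excess in the filgotinib arm is about 0.083 × (25.7 − 8.4) = 1.4 points, which accounts for the rise from 24.9% to 26.4% within rounding. The treatment difference under baseline-only MI is 26.4 − 11.1 = 15.3 points at 10% and 28.1 − 12.4 = 15.7 at 20%, against a true 15.0.

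**3. Bound on the difference.** If every dropout is truly a non-remitter, baseline-only MI gives about p/(1 − d) in an arm with true rate p and missing fraction d.
- d = 10% in both arms: 0.25/0.90 − 0.10/0.90 = 16.7 points
- filgotinib 5%, placebo 20%: 26.3 − 12.5 = 13.8 points
- filgotinib 20%, placebo 5%: 31.25 − 10.53 = 20.7 points

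**4. Effect of the exclusion in Maintenance.** If a share s of would-be missing subjects is already fixed as non-remission, the same bound becomes p/[1 − d(1 − s)]. With an assumed d = 20% in both arms and 40% v 20%:

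| s | Filgotinib | Placebo |
|---|---|---|
| 0 | 50.0% | 25.0% |
| 0.5 | 44.4% | 22.2% |
| 0.8 | 41.7% | 20.8% |
| 1 | 40.0% | 20.0% |

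The excess shrinks as the rule captures more of the poor-outcome dropouts.

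A simulation with an assumed 17% v 31% dropout and correlation 0.7 behaves the same way. Baseline-only MI gives 44.9% v 26.1% with none captured, 40.4% v 21.4% with the worst-scoring half captured, and 38.3% v 19.2% with 80% captured.

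**The case against.** The strongest reply is the exclusion. The subjects whom the plan itself identifies as doing badly are never imputed. As recorded non-remitters they also lower the rates from which others are imputed. A reader might infer that item 4 imputes poor-outcome dropouts at completers' remission rates, or that Maintenance rates are overstated by 4 to 5 points. The opening of SAP 6.2.4.3 does not support either reading. The 4-to-5-point figure appears only if the exclusion is ignored.

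The exclusion still leaves a gap. In Induction the worsening rule does not apply, and Appendix 5 requires starting or escalating specified drugs. In Maintenance the score-based rule needs a rise of at least 3 points to at least 5 on two consecutive visits (or to 9 if the Week 10 value exceeds 6). EBS remission is lost with a rectal bleeding subscore of 1. SAP 6.1 itself has a category for subjects whose endpoint is undetermined after stopping drug for other reasons.

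Second, the treatment difference barely moves in the Induction simulations, and no primary or multiplicity-controlled conclusion depends on item 4. This stands. Nor do the documents support an inference that item 4 flatters filgotinib: the direction depends on dropout by arm, which they do not give.

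Third, a reader might infer that the Maintenance model ignores Week 10 status. SAP 6.2.1 fixes screening values for evaluating remission, not for imputation. SAP 6.2.4.3 itself uses re-baseline MCS and endoscopic subscore in its Maintenance missing-data summaries. This is an ambiguity, not a demonstrated error.

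Fourth, six Maintenance visits would overload a model with about 0.20 × 95 = 19 expected placebo events. This is right, and it shapes the fix.

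**Conclusion.** The concern holds for dropouts not already classed as treatment failure or disease worsening: mainly in Induction, less in Maintenance. For them item 4 ignores collected stool frequency, rectal bleeding and PGA scores and rests on an implausible missing-at-random assumption. At an assumed 10% Induction dropout, filgotinib dropouts are imputed at about 26% instead of 8%, and each arm's rate rises by a little over one point.

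The Induction figures are themselves towards the upper end, since treatment failure would capture some of these subjects. They rest on assumed dropout rates, an assumed correlation of 0.7 and an assumed dropout mechanism. The primary NRI analysis and the item 3 worst case stand as they are. The change is worth making because it is cheap and item 4 is the plan's only model-based missing-at-random analysis.

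**What to change.** In SAP 6.2.4.3 item 4:

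- **Induction:** add post-baseline stool frequency and rectal bleeding subscores (or partial MCS) at Weeks 2, 4 and 6, imputed sequentially by visit before EBS remission.
- **Maintenance:** use a parsimonious form, such as the last available on-treatment score, because placebo events are few.
- **Maintenance baseline:** state that the EBS subscores in the model are the Week 10 (re-baseline) values. Naming Week 10 also settles stool frequency and rectal bleeding, for which SAP Table 3-4 allows Week 10 or Week 11.
- **Treatment failures:** Appendix 5 sets efficacy data to missing after failure. Say how subjects fixed as non-remitters enter the model fit when their later scores are blank.

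The cost is SAP wording, slightly more programming and a somewhat larger imputation model. No new data are needed.
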